A. Title

Assessment of low-cost temperature monitoring tools for neonates.

B. Investigators

Principal Investigator: [name], College of Medicine, Blantyre, Malawi

Co-Investigators: [name], Dept. of Bioengineering, Rice University, Houston, TX USA
[name], Dept. of Bioengineering, Rice University, Houston, TX, USA
[name], Rice 360: Institute for Global Health, Rice University, Houston TX, USA
[name], Rice 360: Institute for Global Health, Rice University, Houston TX, USA
[name], Rice 360: Institute for Global Health

Investigators' CVs: Please see Appendix 1

C. Institutions under whose umbrella the research project will be conducted

- [i] College of Medicine, Blantyre, Malawi
- [ii] Rice University, Houston, TX, USA

D. Executive summary

Problem statement: Neonatal hypothermia is a pervasive global challenge; as many as 85% of infants born in hospitals in low-resource settings are too cold (defined as a temperature <36.5C) [1]. A recent study of 23,240 newborns in Nepal showed that babies with moderate hypothermia are nearly five times more likely to die than normothermic infants; the risk of death is more than 23 times higher for babies with severe hypothermia [2]. While the risks of being too cold are well recognized, hypothermia remains a largely invisible problem in overcrowded newborn units in low-resource settings. Electronic temperature monitors used in high resource settings are not available in low-resource settings because they are too costly or require a constant supply of consumable thermistors. Simple digital or analog thermometers are often unavailable; when they are available, wards are often too short-staffed to permit routine monitoring at regular intervals.

Aim of Study: A team of researchers at Rice University and QECH are working to develop a low-cost temperature sensor that can continuously monitor an infant's temperature (NTM). This robust, low-cost device will allow for the individualized monitoring of each infant with alerts for hypo and hyperthermia. A reusable band to

hold the temperature sensor will eliminate disposable components. This study will assess the accuracy of this novel device against a gold standard along with existing low cost temperature monitors, ThermoSpot and Bempu, to determine which tool is most accurate and effective for neonatal wards.

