The user interface of the device was designed with feedback from Malawian doctors and nurses. The baby's temperature is displayed continuously on the battery powered control box; if the infant's temperature drops below 36.5°C , a blue light atop the box flashes to signal that intervention is necessary. Similarly, if the infant's temperature exceeds 37.5°C , a red light flashes signaling for intervention. The light flashes speed up with degree of hypo- or hyperthermia.

NTM has important advantages compared to two other approaches which have been developed to address this need (Table 1). Unlike Bempu, a wrist-worn monitor that provides an audible alarm, NTM is placed over the liver to measure core temperature and it displays temperature continuously. Neonatal nurses on our development team identified

Table 1: Options for low cost neonatal temperature monitoring

	NTM	Bempu	ThermoSpot
Benefits	Easy to understand continuous visual cues and digital temperature display, no disposables	Audiovisual alarm, intuitive, also suitable for in home use	Visual cue for different levels of hypothermia, low cost, no power required
Cost	\$10	\$30 (2000 Rs) Bempu.com	\$0.50 Maternova.net

temperatures above 36.5°C, brown between 35.5 and 36.4°C, and black below 35.5°C) it is not reusable and the color change can go unnoticed without scheduled monitoring.

In this study we plan to evaluate the ability of NTM, Bempu, and ThermoSpot to detect hypo- and hyperthermia in neonates by comparing to a gold standard electronic temperature monitor used in high-resource settings.

F. Rationale/Justification for the research project

Together, prematurity and infection account for more than 50% of neonatal mortality globally, resulting in a combined 1.7 million deaths each year [5]. Improved ability to monitor neonatal temperature could help improve outcomes for both preterm babies, who are at high risk of hypothermia, as well as babies with infections, who are at high risk of hyperthermia. In many low-resource settings, routine monitoring is simply not possible due to staff and equipment shortages. Our innovation, NTM, offers an affordable, rugged, low-power tool that provides constant monitoring with digital display of temperature and a simple light to notify a guardian or nurse when intervention is necessary. Furthermore, NTM is reusable, requires no consumables, and has a very simple design to facilitate easy maintenance and repairs.

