1. Prior to the start of the study, all study nurses/clinicians will receive training on how to use the test devices. Clinical decisions will still be based on the standard of care, which will not be interrupted during the study. The study nurse/clinician will apply the temperature sensors to the infant.
2. A research technician will be available for the duration of the study to record the data from the monitors.

Enrollment :

Enrollment will take place after fully informed and written consent from the parent or guardian. A parent will be free to withdraw their child from participating at any time, without explanation and without detriment to ongoing care. There will be no financial benefit to participants though the infants will benefit from close monitoring. A participant identification number will be assigned. This number will be used for identification purposes throughout the study.

Monitoring of Neonates:

During the trial, the following steps will be taken:

A trained study nurse will assess the subject for clinical complications before attaching the temperature monitoring device.

- 1) A trained study nurse or clinician will attach the three test temperature monitoring devices to the infant. A trained research assistant from Rice University or from the Biomedical Engineering Department at Malawi Polytechnic will observe all procedures and will notify the nurse of any observed errors so they may be corrected. They will also be able to answer any technical questions from the nurse.
- 2) The trained study nurse will attach the temperature probe from the commercial gold standard as well as provide any other care needed.
- 3) A research assistant will use a laptop to collect data from the continuous temperature monitors (NTM and gold standard). The nurse will record the temperature readings every hour from all monitors on paper forms along with the standard of care.
- 4) Each time an alarm sounds from any device (Bempu and the commercial gold standard have audible alarms), the nurse will record all temperature values including a reading taken with the standard of care method. If the subject is found to be hyper/hypothermic, the nurse will respond with the appropriate standard of care.
- 5) Temperature monitoring will continue for up to 3 days. The research assistant may ask the nurse to remove and reapply the temperature probes during this period.

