A research assistant will be available during the trial to mitigate any complications with the devices. If the subject's guardian, the nurse, or the research assistant indicates concern during the tests, temperature monitoring will be discontinued and the subject's treatment will return to the standard of care. The nurse can choose to remove one of the test devices and continue the study with the remaining monitors if any issue arises.

Clinical data will be collected on paper forms as is consistent with current clinical practice. Data from the temperature monitors will be saved on a secure study server for analysis. Clinical and/or research personnel will record information, excluding personal identifiers, on a standardized patient monitoring form. After the subject's participation is complete, a research assistant will collect and scan the form.

The following section details the variables that will be measured or calculated in the study.

Intended Data Collection:

1. Baseline demographic and relevant medical information
 - a. Recorded once at enrollment
 - i. Date of Study
 - ii. Date of Birth
 - iii. Sex
 - iv. Birth Weight
 - v. Type of delivery
 - vi. Gestational age at birth
 - vii. Corrected gestational age
 - viii. Abdominal circumference
 - ix. Admission Temperature
 - b. Recorded throughout study as clinically collected
 - i. Other comorbidities
 - ii. Medications/treatments given
 - iii. Current weight
 - iv. Additional temperature measurements taken as standard of care
2. Accuracy
 - a. Recorded automatically by study equipment
 - i. Abdominal temperature and alarms from Rice designed temperature monitor and gold standard device
 - b. Recorded every hour by study nurse or as alarm events occur
 - i. Temperature measurements from other devices
 - ii. Temperature measurements using standard of care method (axillary)
 - iii. Ambient temperature
 - iv. Current thermal treatment, if any
 - c. Movement/other caregiving
 - d. Fit/tightness of the devices

A log of observed user error and comments may be used to improve the usability of the test devices.

[vii] Data Management and Analysis

Personal identifiers will be removed from the data which will be kept on a secure server accessible only to study personnel.

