The accuracy of the temperature sensors will be determined by calculating the difference between the temperatures recorded by the temperature sensor and the commercial patient monitor at each point in time. The average error between the temperature sensor and the gold standard will be calculated for each subject and compiled in a Bland-Altman plot. The 95% limits of agreement will be calculated. Our target error is less than +/- 0.5 C.

For the devices that do not provide a continuous numerical reading, the recorded state every hour will be compared to the gold standard at that point in time. The sensitivity and specificity for hypo/hyperthermia will be calculated for each device.

The ability of each device to accurately diagnose hypothermia will also be calculated with respect to the alarm events for each device for which they were recorded. The sensitivity and specificity will be determined using the number of false alarms collected during the study.

As a secondary analysis, the errors will be plotted against thermal treatment type and ambient temperature to determine their confounding effects on accuracy. An ANOVA will be used to determine statistical significance.

The research team from Rice University and QECH will be responsible for all data analysis. We plan to analyze data using Excel, MATLAB, and associated statistics packages.

[viii] Results Presentation

Statistical analysis will be performed and means, limits of agreement, sensitivities and specificities will be reported. Tables and graphs may also be used to present any additional correlations, explain outliers, or demonstrate confounding effects.

[ix] Dissemination of Results

The results of this study will be made available to the Ministry of Health, COMREC, the College of Medicine Library, the Department of Paediatrics, and other partners working in neonatal and child health. A copy of the final report and any published papers or abstracts will be submitted to The Health Sciences Research Committee and the University Research and Publication Committee (URPC) through the COMREC Secretariat. Findings will be published in academic journals and conference

proceedings in an effort to disseminate results to potential end-users. The research findings of this study will be critical in the evaluation of future interventions.

I. Ethical considerations

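### A count of false alarms cannot give alarm-event sensitivity, and gives specificity only with a true-negative count that the plan does not define

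*Combined protocol and SAP*

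**What the plan says.** Section H [vii] (Data Management and Analysis) of the combined protocol and SAP plans two analyses of sensitivity and specificity.

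- **Hourly.** For devices without a continuous numerical display, "the recorded state every hour will be compared to the gold standard at that point in time". This covers both hypo- and hyperthermia.
- **Alarm events.** Each device's ability to diagnose hypothermia is assessed "with respect to the alarm events for each device for which they were recorded", and "The sensitivity and specificity will be determined using the number of false alarms collected during the study".

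Section H [vi] sets what is collected. In step 3 of Monitoring of Neonates, NTM and the gold standard are logged continuously to a laptop, and all monitors are read hourly. In step 4, "Each time an alarm sounds from any device (Bempu and the commercial gold standard have audible alarms), the nurse will record all temperature values". Item 2 of Intended Data Collection adds automatic recording of temperature and alarms for NTM and the gold standard. It heads the nurse's readings "Recorded every hour by study nurse or as alarm events occur". NTM signals by light: below 36.5 °C, "a blue light atop the box flashes to signal that intervention is necessary" (section E).

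Section D defines hypothermia as below 36.5 °C. Section E gives NTM's alert limits as 36.5 and 37.5 °C. No alarm limits are given for Bempu or the gold standard. Section H [viii] says that sensitivities and specificities will be reported.

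**The concern.** The only count that the alarm-event rule names is false positives. That count cannot produce sensitivity, and it produces specificity only once someone decides what a true negative is and in what unit it is counted. The plan leaves both open, and also does not say whether an alarm is judged false against the gold standard or against the axillary reading. The analyst would have to choose after the data are in.

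The alarm setting adds a second difficulty: moments enter the data because a device alarmed. A table built from such moments depends on which devices alarm and at what limits, as well as on the accuracy of the device being assessed. The study compares three devices and the figures are to be published, so a selection effect could be read as a property of a device.

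**Working it through.** The plan states no target or expected sensitivity or specificity, so there is no figure of its own to reproduce. The check is by definition, followed by an illustration.

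**1. What a false-alarm count determines.** Sensitivity = TP/(TP+FN); specificity = TN/(TN+FP); a false alarm is FP. Take 30 false alarms (assumed).

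- Sensitivity is 90/(90+10) = 90%, 50/(50+50) = 50% or 10/(10+90) = 10%, depending on TP and FN. The 30 plays no part.
- Specificity with TN = 0, 10, 30, 100 or 300 is 0%, 25%, 50%, 77% or 91%, for example 10/(10+30) = 25%.

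**2. A device's own alarm events.** Every event is an alarm, so FN = 0 and TN = 0. Sensitivity is 100% and specificity 0%, however good the device is.

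**3. All records made under step 4.** For Bempu, every TP and FP is recorded, because Bempu's own alarm triggers the record. A Bempu true negative is recorded only if another device alarms at that moment. Recorded TN therefore cannot exceed total TN, and specificity can only fall. Bempu's missed events are all recorded if the gold standard's low limit is at or above 36.5 °C, and sensitivity is then unbiased. With a lower limit some misses are lost and sensitivity is too high.

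**4. Illustration.** From the documents: at most 60 infants, at most 3 days, the 36.5 °C threshold and the NTM limits. Assumed: gold-standard readings normal with mean 36.7 and SD 0.5 °C; independent Bempu and NTM errors with SD 0.3 °C; Bempu alarm below 36.5 °C; gold-standard limits 36.5 and 37.5 °C.

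- Infant-hours: 60 × 72 = 4,320.
- Share hypothermic: Φ((36.5 − 36.7)/0.5) = Φ(−0.4) = 0.345.
- Bempu hours by numerical integration: TP 1,186, FN 302, FP 394, TN 2,437 (the sum is one short through rounding).
- All time: sensitivity 1,186/1,488 = 0.80; specificity 2,437/2,831 = 0.86; positive predictive value 1,186/1,580 = 0.75.

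| Records used | TN kept | Bempu specificity |
|---|---|---|
| All monitored time | 2,437 | 2,437/(2,437+394) = 0.86 |
| Audible alarms only | 237 | 237/(237+394) = 0.38 |
| Audible alarms and NTM alerts | 707 | 707/(707+394) = 0.64 |

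Sensitivity on these records stays at 0.80 with a gold-standard low limit of 36.5 °C. With a limit of 36.3 °C it is 0.93 (audible only) or 0.84 (with NTM alerts). With 36.0 °C it is 0.995 or 0.85.

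**5. Dependence on the unknown limit.** I used 18 scenarios (mean 36.5, 36.7 or 36.9; SD 0.4, 0.5 or 0.6; error SD 0.2 or 0.3) with a high limit of 37.5 °C and NTM alerts triggering records. The smallest shortfall in specificity is 0.11 with a low limit of 36.5 °C, 0.08 with 36.7 °C and 0.03 with 37.0 °C. The direction does not change, but the gap shrinks as the limit rises.

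**6. Data that could fill the table.** For NTM, the two continuous logs can supply all four cells. For Bempu and ThermoSpot, the scheduled hourly readings can. The plan collects all of these but does not link them to the alarm analysis.

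**The case against.** The best defence is that this is one loosely worded sentence. It does not say that false alarms are the only input. For NTM, the automatic log of temperatures and alarms may be exactly what is meant by recorded alarm events, and the hourly Bempu states could supply true negatives. The study is a pilot with no target for sensitivity or specificity, and its main accuracy results come from elsewhere.

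Much of this stands. The data are not missing; what is missing is a rule that connects them to the analysis. A reader might infer that Bempu's alarm specificity is bound to be biased. The documents do not support that, because they never say that the table will be built from the step 4 records alone. A reader might also infer that the alarm-based and hourly specificities could differ only through the selection of moments. That does not follow either: the hourly analysis covers hypo- and hyperthermia while the alarm analysis covers hypothermia, and the units differ.

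The objection does not rescue the sentence itself. As worded, the rule names a count that is irrelevant to one of its two quantities and insufficient for the other.

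**Conclusion.** The point holds as a faulty analysis rule of limited reach, and should be corrected before analysis. That false alarms do not enter sensitivity, and give specificity only with an undefined true-negative count, follows from the definitions and needs no assumption. The downward bias in Bempu's specificity is conditional on a table built from alarm-triggered records. Given that, its direction holds for any alarm limits. The upward bias in sensitivity needs, in addition, a gold-standard low limit below 36.5 °C.

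The sizes (0.86 against 0.38 or 0.64) rest on an assumed temperature distribution, device error and alarm limits, and show only that the effect can be large. The 0.11 should not be read as a general minimum, since it applies to one assumed limit. Nor does counting in minutes bring specificity close to 1 in this model: the 394 are false-alarm hours, and dividing them by minutes mixes units.

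The hourly analysis, the Bland-Altman analysis and the paired readings at alarms (objective 1c) are unaffected. No decision rule or sample-size figure uses the alarm results.

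**What to change.** Replace the sentence in section H [vii] with:

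> For hypothermia alarm events we will report, for each device with recorded alarms (NTM from its automatic log, Bempu from the step 4 records), the positive predictive value against the gold-standard reading at the time of the alarm and the number of false alarms per infant-hour monitored with that device. An alarm event is one continuous alarm, with repeat alarms merged by an interval set before analysis. Confidence intervals will allow for repeated events within an infant. Sensitivity and specificity for hypothermia will be taken only from data not triggered by alarms: the continuous NTM and gold-standard logs, and the scheduled hourly readings for Bempu and ThermoSpot.

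Keep alarm-triggered records identifiable, so that they do not enter the hourly analysis. Note the alarm limits in force on Bempu and the gold standard. Note also when each device is removed or reapplied: section H [vi] allows both, the list of data to be collected has no such times, and the false-alarm rate needs them for its denominator.

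The cost is a little more analysis work and some annotation on the monitoring form. The readings and logs are already to be collected, and care of the infants does not change.

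### The ANOVA of errors on thermal treatment and ambient temperature names no unit of analysis or infant effect; if hourly readings are pooled, its p-values are invalid

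*Combined protocol and SAP*

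**What the plan says.** Section H [vii] (Data Management and Analysis) obtains the error by "calculating the difference between the temperatures recorded by the temperature sensor and the commercial patient monitor at each point in time", so each infant contributes many errors. One aggregation is then described: "The average error between the temperature sensor and the gold standard will be calculated for each subject and compiled in a Bland-Altman plot".

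For the secondary analysis the same section says that "the errors will be plotted against thermal treatment type and ambient temperature to determine their confounding effects on accuracy", followed by "An ANOVA will be used to determine statistical significance". Nothing else in the document specifies this test. It gives no significance level, no statement of whether an observation is a reading or an infant mean, and no term for the infant.

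Section H [vi] (Intended Data Collection, item 2b) lists ambient temperature and "Current thermal treatment, if any" under the heading "Recorded every hour by study nurse or as alarm events occur". Step 5 of Monitoring of Neonates states: "Temperature monitoring will continue for up to 3 days". Section H [v] allows up to 60 infants, up to 30 from the neonatal ward and 30 from the KMC ward.

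**The concern.** The data are clustered by design, and the plan does not say how the test deals with that. Averaging per subject is tied to the Bland-Altman plot. The secondary analysis speaks only of the errors, and its two factors are recorded hourly and can change during an infant's stay. An analyst following this text would most naturally put all readings into one ANOVA. That test assumes independent observations, yet readings from one infant share that infant and, between reapplications, the fit of the device. Neighbouring hours are also likely to be correlated.

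The alternative, an ANOVA of per-infant means, would hold its error rate. It would, however, discard the within-infant changes in treatment and ambient temperature that the hourly record captures. Two analysts could therefore obtain different p-values from the same data.

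At stake is a false report that thermal treatment or ambient temperature affects accuracy, when only infant-to-infant or hour-to-hour variation is present.

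**Working it through.** The plan has no figure to reproduce: it states no alpha, standard deviation, effect size or intra-infant correlation (ICC) for this test.

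**Inputs from the plan.** Up to 60 infants; hourly readings for up to 3 days, so m = 3 × 24 = 72 scheduled readings per infant and 60 × 72 = 4,320 in total.

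**Assumptions.** Nominal alpha 5%; no true effect; error = infant effect (variance ICC) + residual (variance 1 − ICC), with the residual either independent or AR(1). The ICC, lag-1 correlation and treatment pattern are varied. Simulations used 2,000 runs per setting unless noted.

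**1. One treatment per infant (10/10/10/30 infants), independent residuals.** The design effect is DE = 1 + (m − 1) × ICC and the effective sample size is 60m/DE. With four treatment groups, the F statistic multiplied by its 3 degrees of freedom is inflated by about DE. The rejection rate is therefore about P(χ²₃ > 7.815/DE).

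| m | ICC | DE | Effective n | 7.815/DE | Approximate type I error | Simulated |
|---|---|---|---|---|---|---|
| 72 | 0.01 | 1.71 | 2,526 | 4.570 | 21% | 21% |
| 72 | 0.05 | 4.55 | 949 | 1.718 | 63% | 64% |
| 72 | 0.10 | 8.10 | 533 | 0.965 | 81% | 81% |
| 72 | 0.20 | 15.2 | 284 | 0.514 | 92% | 92% |
| 72 | 0.30 | 22.3 | 194 | 0.350 | 95% | 95% |
| 24 | 0.01 | 1.23 | 1,171 | 6.354 | 10% | 10% |
| 24 | 0.05 | 2.15 | 670 | 3.635 | 30% | 33% |
| 24 | 0.10 | 3.30 | 436 | 2.368 | 50% | 51% |
| 24 | 0.20 | 5.60 | 257 | 1.396 | 71% | 71% |
| 24 | 0.30 | 7.90 | 182 | 0.989 | 80% | 83% |

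The approximation and the simulation agree. An ANOVA of infant means gave 4-6%.

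**2. Treatment changes within infant (72 readings, ICC 0.05 to 0.30).**
- Nursery infants rotate through three treatments in random order, one third of the stay each, and KMC infants stay fixed: 29% to 59% with independent residuals, 80-84% with lag-1 correlation 0.8.
- Nursery infants only, balanced rotation: 2-4% with independent residuals, 52-62% with lag-1 correlation 0.8.
- Three treatments and one switch per infant at a random time, independent residuals (1,500 runs): 33% at ICC 0.05 and 76% at ICC 0.30.

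**3. Ambient temperature as a continuous covariate, 72 readings.**
- Half its variance between infants: 23%, 37% and 55% at ICC 0.05, 0.10 and 0.30.
- Only a daily cycle within infant: 2-5% with independent residuals, 26-28% with lag-1 correlation 0.8.

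**4. Candidate remedies, 72 readings.**
- A REML mixed model with infant intercept plus AR(1) residuals (250 runs per setting, Monte Carlo standard error √(0.05 × 0.95/250) ≈ 1.4 points) gave 3-6% in all eight settings: ICC 0.05 or 0.30, lag-1 0 or 0.8, fixed or rotating treatment.
- An infant intercept alone gave 59-60% in the rotating design with lag-1 correlation 0.8.
- Infant-clustered standard errors gave 6-8% (rotating, KMC fixed) and 4-7% (ambient temperature).

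**The case against.** **Pooling is not stated.** The only aggregation the section describes is per subject, and the word ANOVA does not exclude a repeated-measures version. On infant means there is no type I error problem. This stands as far as it goes: the defect is an unspecified unit, and the inflation is conditional on pooling. But the averaging sentence concerns the Bland-Altman plot, and an infant mean cannot be assigned a single treatment or ambient temperature when these change during the stay.

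**The direction can reverse.** This stands. With treatment balanced within infants and independent residuals, the pooled test is conservative and loses power. It inflates when treatment is constant or changes rarely within an infant, or when errors are serially correlated. KMC is a separate ward with up to 30 of the 60 infants, so treatment is probably fixed for many of them.

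**The size rests on assumptions and ceilings.** This also stands. The plan gives no ICC, and 60 infants and 3 days are maxima. A range from 2% to 95% does not locate this study, although with one treatment per infant even 24 readings and an ICC of 0.05 give about a third.

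**The test matters little, and AR(1) is too specific.** It is secondary, in a pilot, and no stated decision depends on it. It probably concerns NTM alone among the test devices, since Bempu is described by its alarm and ThermoSpot by its colour. That limits the weight but does not make the test valid. On the remedy, probes may be reapplied, so fit can change within an infant. Alarm-time readings are unevenly spaced. The AR(1) model was checked only on data generated under that structure. These are reasons to keep clustered standard errors as an alternative.

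**Conclusion.** The concern holds. The plan specifies a significance test on repeated readings without a unit of analysis or an infant effect. If readings are pooled, the p-values ignore within-infant correlation. Under the assumptions above, the type I error at a nominal 5% with 72 readings is 21% to 95% when treatment is constant within infant (ICC 0.01 to 0.30), and 29% to 84% in the rotating design with KMC fixed. It is at or below nominal only where the factor varies purely within infants and residuals are independent. The treatment figures agreed to within a few points on repetition; the ambient-temperature and mixed-model figures rest on one set of simulations each.

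The point should be corrected, but its reach is limited. It concerns a secondary analysis in a pilot study and leaves the limits of agreement, sensitivity and specificity unaffected.

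**What to change.** Replace the ANOVA sentence with a linear mixed model on the paired hourly errors (device minus gold standard), fitted for each device that gives numerical readings. Include:
- thermal treatment as a categorical effect and ambient temperature as a continuous effect;
- a random infant intercept and AR(1) residuals, because the intercept alone is not enough if treatment changes within infant and errors are serially correlated;
- a stated significance level.

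Infant-clustered standard errors are an acceptable alternative, and the more practical one if the chosen software does not fit serially correlated residuals or if alarm-time readings are included. Optionally, repeat the model on absolute error, so that loss of precision is tested as well as a shift in the mean.

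The cost is one replaced sentence and one model per numerical device, with no new data; the plan already allows MATLAB and associated statistics packages. The downsides are a little more analysis, usually larger p-values, and, with clustered standard errors and 60 infants, an error rate slightly above nominal (6-8% in the rotating design).
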